11.17 Safety Monitoring

11.17.1 Data and Safety Monitoring Board (DSMB)

An independent CTN DSMB will examine accumulating data to assure protection of participants' safety while the study's scientific goals are being met. The CTN DSMB is responsible for conducting periodic reviews of accumulating safety and efficacy data. It will determine whether there is support for continuation of the trial, or evidence that study procedures should be changed, or if the trial should be halted, for reasons relating to the safety of the study participants, the efficacy of the treatment under study, or inadequate trial performance (e.g., poor recruitment).

11.17.2 Adverse Events (AEs)

The Site PI may appoint one or more Site Physicians/Medical Clinicians (MD, DO, or other medical clinician with DEA waiver or licensure to prescribe/dispense buprenorphine for treatment of opioid use disorder) for this study, who will review or provide consultation for each SAE, as needed. These reviews will include an assessment of the possible relatedness of the event to the study intervention or other study procedures. The Site Physicians/Medical Clinicians will also provide advice for decisions to exclude, refer, or withdraw participants as required. In addition, NIDA will assign a Medical Monitor to this protocol to independently review the safety data, present it to the DSMB for periodic review, and provide PIs a Safety Letter when necessary. The Medical Monitor will determine which safety events require expedited reporting to NIDA, the DSMB, pharmaceutical, and regulatory authorities. This will include events that are serious, related, and unexpected. The study staff will be trained to monitor for and report AEs and SAEs. Additionally, as applicable, sites will submit reporting of AEs/SAEs according to IRB requirements. Each of the sites has established practices for managing medical and psychiatric emergencies, and the study staff will continue to utilize these procedures. Treatment providers at each site will be responsible for monitoring participants for possible clinical deterioration or other problems, and for implementing appropriate courses of action.

Safety for this study will be monitored through specific study assessments and medical record abstraction in addition to more standard AE/SAE reporting.

The Hospital Anxiety and Depression Scale (HADS): The Hospital Anxiety and Depression Scale (HADS)¹¹⁷ will be used to assess for symptoms of depression and anxiety. Participants who score in the range for possible depression (total depression score of 8 or higher) or anxiety (total anxiety score of 8 or higher) will be assessed by a qualified clinician before leaving the visit as specified in the site clinical SOP. For visits held via telemedicine or at an external location, research staff will contact a qualified clinician via phone to coordinate an assessment via telemedicine as quickly as possible; ideally this assessment will occur while the staff and participant are together at the external location.

Prior/Concomitant Medications: All medications taken by the participant since the start of her pregnancy and during the active study will be documented on a Prior/Concomitant Medications assessment (see **Table 3**).

Fetal Outcomes: Gestational age at outcome, spontaneous abortions/miscarriages, stillbirth, pregnancy terminations and indications for termination.

Maternal Delivery Outcomes: Unplanned cesarean section, abnormal fetal presentation during delivery, medical complications at delivery, and analgesic receipt during labor and delivery, postpartum, and upon discharge.

Birth/Neonatal Outcomes: Birth/neonatal outcomes will be abstracted from the medical record. These outcomes include: head circumference, weight and length at birth, gestational age at delivery, and 1-minute and 5-minute Apgar (activity, pulse, grimace, appearance, respiration) scores. Other outcomes will include: major birth defects, stillbirth, neonatal death, and need for resuscitation. Adverse birth outcomes will be characterized, including (if preterm), the reason for preterm birth (e.g., fetal distress, etc.). Other adverse neonatal outcomes will be captured including respiratory distress symptoms, need for respiratory support in the neonatal unit, feeding problems (e.g., need for nasogastric tube), seizures, and other co-morbidities.

Injection Site Examination: Participants will be asked to immediately report any injection site reactions to study staff for evaluation, monitoring, and possible referral, as needed. For weekly injections, the site of the last BUP-XR injection will be examined at the weekly Medication Check Visits. For monthly injections, the BUP-XR injection site will be examined at the weekly Medication Check Visit following the visit during which the injection was given. Injection Site Examinations must be performed in-person. Injection site reactions will be documented on the Injection Site Reaction Reporting form.

Opioid Overdose Tracking: During the study, the participant will complete a self-report assessment about opioid overdose as outlined in **Table 3**. If a participant reports an overdose, research staff will refer her to the clinic staff who will follow up each case as specified in the site clinical SOP.

Infant Sedation: Infant sedation will be assessed via mother-report as outlined in **Table 3**. The infant sedation assessment will be completed by participants who are feeding their infants with breastmilk and/or formula and will assess for signs of infant sedation (e.g., not waking for feeding, difficulty breathing, etc.).

Bayley™-4. The Bayley™-4¹⁰² includes cognitive, language, fine motor, and gross motor subscales.

Child Behavior Checklist (CBCL). The CBCL¹⁷⁴ is administered to caregivers and includes items that describe behavioral, emotional, and social problems that characterize preschool children.

Events related to withdrawal symptoms will be captured on the SOWS-Gossop and will not be duplicate-reported on an AE form. However, precipitated withdrawal during study medication induction will be reported as an AE. Events captured on study specific forms (e.g., HADS) will not be recorded separately as an AE, unless they meet the SAE definition. Any of these events that meet the definition of an SAE, during the reporting periods described below, will be reported on the AE/SAE form set.

Adverse Events and Serious Adverse Events:

For the purpose of this study and if not described above, these events are required to be reported as an AE/SAE:

- All deaths that occur in either the Mother or the Infant (SAE)
- Congenital anomaly observed (SAE)
- Other infant SAEs that occur in breastfed infants
- All maternal AEs/SAEs while on study, except as noted below in “Events that do not require AE/SAE reporting”
- Maternal hospital re-admission within 6 weeks of delivery (SAE)
- Any ICU admission during the Labor and delivery admission (SAE)
- An opioid overdose resulting in naloxone rescue (SAE)

Events that do not require AE/SAE reporting:

- Hospitalization for Labor and Delivery, unless the hospitalization results in an ICU admission
- Prolongation of the hospital stay for a delivery (unless greater than 4 days for vaginal delivery or 7 days for C-section delivery)
- Admission to a hospital for elective surgery or pre-scheduled diagnostic tests
- Opioid overdose, unless resulting in naloxone rescue, hospitalization, or death
- Infant AEs and SAEs, except infant deaths, congenital anomalies in all infants, , and other infant SAEs in breastfed infants

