4.3.2 Medication Check Visits vs. Research Visits

In a pragmatic trial, research assessments/interactions that could impact outcomes and, thus, reduce the generalizability of the results to real world practice are minimized. However, this goal must be balanced with the need to closely monitor safety given that CTN-0080 is the first trial to evaluate the BUP-XR formulation in pregnant women. This balance will be achieved by including weekly Medication Check Visits, which include a minimal number of assessments and procedures (see **Table 3**), while limiting more intensive data collection to Research Visits, which will occur less frequently (e.g., monthly during pregnancy, etc.; see **Table 3**).

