
7.2.1.2 *Drug and Alcohol Abstinence*

Drug and alcohol abstinence during pregnancy and postpartum are secondary outcomes and will be assessed in a fashion similar to the assessment of illicit opioid abstinence, but rather than being restricted to illicit opioid use, will include alcohol and other drugs of abuse. Missing urine samples will be imputed as positive.

7.2.1.3 *The Opioid Craving Scale*

Craving will be assessed with the Opioid Craving Scale, which was utilized in CTN-0030 and shown to have predictive validity.¹¹² The total score is calculated by averaging the scores from three visual analogue scales which assess craving, cue-induced craving, and likelihood of using.

7.2.1.4 *Adequacy of Prenatal Care Utilization*

Kotelchuck's Adequacy of Prenatal Care Utilization (APNCU) index,¹¹³ which is a well-established index,¹¹⁴ will be used to assess the adequacy of prenatal care. The APNCU includes two indices that are combined to obtain a total score. One index is the timing of prenatal care initiation scored in 4 categories [EGA months: 1) 1 and 2; 2) 3 and 4; 3) 5 and 6; and 4) 7 to 9]. The second is the ratio of observed to expected visits based on the length of time between the first prenatal care visit and delivery, scored in 4 categories: 1) Inadequate (received less than 50% of expected visits); 2) Intermediate (50%-79%); 3) Adequate (80%-109%); 4) Adequate Plus (110% or more). The information for the APNCU will be derived from either medical records or the birth certificate. The % of expected visits attended prior to study randomization will be included as a baseline covariate in analyses.

7.2.1.5 *The Short Opiate Withdrawal Scale (SOWS)-Gossop*

The SOWS-Gossop¹¹⁵ will be used to measure opioid withdrawal symptoms. The SOWS-Gossop, which is a self-administered scale that includes 10 items, rated on a scale of 0 (none) to 3 (severe), is a validated instrument with good reliability.¹¹⁶ It will be completed following the schedule in **Table 3**.

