8.4 Randomization Plan

Eligible participants will be randomized in a 1:1 ratio to BUP-XR or BUP-SL. The randomization process will be performed by computer by the Data and Statistics Center (DSC). A permuted block randomization procedure with random block sizes will be implemented to balance on site, whether participants are on BUP-SL at the time of randomization (yes vs. no), and EGA at time of randomization (6 weeks - 18 weeks vs. 19 weeks - 30 weeks); EGA was used as a stratification variable in the MOTHER trial.⁴³

Table 3: Overview of Assessments and Procedures																			
Perinatal Phase:	Pregnancy					Delivery & Immediate Post-partum	Post-partum												As Needed
	Pre- Screen	Screen/ Base ¹	Random- ization ²	Week 3	Monthly Post-rand ³		Month 1	Month 2	Month 3	Month 4	Month 5	Month 6	Month 7	Month 8	Month 9	Month 10	Month 11	Month 12	
Research Visits		X	X	X	X		X		X			X			X			X*	
Screening Assessments																			
Pre-screen verbal consent	X																		
Pre-screen interview	X																		
Informed Consent		X																	
Medical record releases		X																	X
Demographics/PhenX Tier 1		X																	
DSM-5 checklist		X																	
PRISM-Suicide/Homicide		X																	
Blood Chemistry ^{4,5}		X																	
Urine Pregnancy Test		X																	
Estimated Gestational Age ^{4,5}		X																	
Treatment and Research Status		X																	
Medical and Psych History (Hx)		X																	
Drop-out Risk Assessment		X																	
Weekly Medication Check Visits ⁶																			
BUP-XR administration/documentation			Weekly administration ⁶				Weekly or Monthly administration ⁷												
BUP-SL dispense/document; adherence			Weekly - Monthly dispensing ⁸				Weekly - Monthly dispensing ⁸												
Adverse Events/Serious Adverse Events			Weekly ⁶				Weekly ⁶												
Injection Site Reaction Reporting Form																			X
Urine drug screen		X	Weekly ⁶				Weekly ⁶												
Infant sedation assessment							Weekly ⁶												
Pregnancy Test (BUP-XR)							Monthly for participants on monthly BUP-XR formulation												X
Medication Check Visit Compensation			\$20 per visit not corresponding to a research visit																
Table 3 continued on next page																			

Table 3 continued on next page

Table 3: Overview of Assessments and Procedures																			
Perinatal Phase:	Pregnancy					Delivery & Immediate Post-partum	Post-partum												As Needed

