All cases of precipitated withdrawal in either study arm will be considered adverse events. All medications given will be captured as concomitant medications. In the event that precipitated withdrawal leads to fetal monitoring, any action taken specifically as a result of the fetal monitoring will be documented.

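### Withdrawal symptoms are kept off the AE form because the SOWS-Gossop is said to capture them, but it is scheduled at only about 26-30% of weekly visits in pregnancy and 9% postpartum, so non-serious withdrawal between those visits may enter neither record

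*Combined protocol and SAP*

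**What the plan says.** Section 11.17.2 sets the rule: "Events related to withdrawal symptoms will be captured on the SOWS-Gossop and will not be duplicate-reported on an AE form". Two exceptions follow in the same paragraph. The first is "However, precipitated withdrawal during study medication induction will be reported as an AE", which section 9.3.1 supports: "All cases of precipitated withdrawal in either study arm will be considered adverse events". The second sends to the AE/SAE form set "Any of these events that meet the definition of an SAE".

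The list of reportable events that comes next includes "All maternal AEs/SAEs while on study, except as noted below in" a list of exempt events. That exempt list does not name withdrawal. However, the reportable list is introduced as covering events not already dealt with earlier in the section, and withdrawal has been.

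Section 7.2.1.5 says the SOWS-Gossop "will be used to measure opioid withdrawal symptoms", refers to Table 3 for its timing, and gives no recall period. Table 3 (section 8.4) has a row "Adverse Events/Serious Adverse Events" marked weekly in pregnancy and postpartum. Its SOWS-Gossop row is marked at screening/baseline, week 3, monthly after randomization, and postpartum months 1, 3, 6, 9 and 12. The as-needed column is blank for the SOWS, although it is used for injection site reactions, pregnancy tests and the mental health follow-up form. The sparser schedule is deliberate: section 4.3.2 describes "limiting more intensive data collection to Research Visits, which will occur less frequently".

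**The concern.** The AE rule hands withdrawal to an instrument that is absent from many of the visits at which AEs are asked about. A woman who mentions withdrawal at week 1 or 2, or at postpartum week 20, has no SOWS scheduled that day, and the section does not tell the site what to record.

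Section 4.3.2 justifies weekly visits by the need to watch safety closely in the first trial of this formulation in pregnancy. Withdrawal is an effect on which the formulations are expected to differ (sections 4.1.3 and 4.1.4). Section 4.4.1 puts BUP-XR steady state at about study days 20-25 and says BUP dropout tends to fall in the first 30 days, while the first SOWS after randomization is at week 3. Section 17.7 names withdrawal on abrupt discontinuation as a study risk.

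The Medical Monitor looks for trends in AEs (section 11.17.3) and the DSMB receives AE listings (section 17.3). The safety analyses in section 10.3.4 cover AEs, HADS, fetal/delivery and neonatal outcomes, but not the SOWS. Withdrawal that is off the AE form and between SOWS visits reaches none of these, and it cannot be recovered after data collection.

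**Working it through.** The plan states no SOWS coverage figure, so there is none to reproduce. Table 4a (section 8.6) supplies visit counts, and its totals were checked first.

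- Low end: 120 + 40 + 7×20 + 2×60 + 48×20 + 240 + 70 = $1,690.
- High end: 120 + 40 + 36×20 + 8×60 + 52×20 + 240 + 70 = $2,710.

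Both match the table.

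**Share of weekly visits with a SOWS** = SOWS time points / (weekly visits without a research visit + research visits). In pregnancy the SOWS points after randomization are week 3 plus the monthly visits (2 to 8 in section 8.6), so 3 to 9.

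- Entry at 30 weeks, delivery at 40 (assumed): 10 weekly visits, 1 + 2 = 3 SOWS, 3/10 = 30%. The Table 4a low end agrees: 3/(7 + 3).
- Entry at 6 weeks, delivery at 40 (the longest case in section 4.2.1): 34 weekly visits, 1 + 8 = 9 SOWS, 9/34 = 26.5%.
- Intermediate entries lie close by. Entry at 18 weeks gives 6/22 = 27%, and entry at 24 weeks gives 5/16 = 31%.
- The Table 4a high end taken literally gives 9/(36 + 9) = 20%, but 45 weekly visits do not fit into 34 weeks, so this is not used.
- Postpartum: 5/(48 + 5) = 9.4%, or 5/(52 + 5) = 8.8%. Section 8.5 places the 12-month visit at week 53, which matches the first.

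**Days covered under an assumed recall period.** A visit share says nothing about how far back the scale looks. With s SOWS points, recall r days and T days of follow-up, the ceiling is min(1, s×r/T). T is 70 days (shortest pregnancy case), 238 days (longest) and 371 days (postpartum, 53 weeks).

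| Assumed recall | Pregnancy, s=3, T=70 | Pregnancy, s=9, T=238 | Postpartum, s=5, T=371 |
|---|---|---|---|
| 1 day | 4% | 4% | 1% |
| 7 days | 30% | 26% | 9% |
| 14 days | 60% | 53% | 19% |
| 28 days | 100% | 100% | 38% |

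The pregnancy columns are ceilings because the week 3 and first monthly windows overlap when recall exceeds 7 days. If monthly visits fall at weeks 4, 8 and so on, 28-day windows cover 56/70 = 80% and 224/238 = 94%. For 14 days, the week 3 and week 4 windows together cover 21 days, giving (21 + 14)/70 = 50% and (21 + 7×14)/238 = 50%. Postpartum windows do not overlap, because the visits are two to three months apart: 5×28/371 = 140/371 = 38%.

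**Before week 3.** No weekly visit before week 3 has a SOWS. A recall of 21 days or more at week 3 would reach back to randomization, but only for women who attend. Section 8.5 asks a woman leaving early to complete the next research visit's assessments if she is willing. Otherwise she contributes no SOWS after randomization.

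**The case against.** The strongest reply is that the rule prevents only duplicates. An event that no SOWS captured is not a duplicate, the neighbouring sentence on forms such as the HADS exempts events actually captured on those forms, and sections 17.2.1 and 17.8 say all AEs are collected. On that reading a site should report uncaptured withdrawal. This stands as a possible reading, so the text should not be called an outright prohibition. It does not settle the matter: the withdrawal sentence carries no such condition, and the general duty to report maternal AEs is limited to events not already dealt with. Sites could reasonably differ.

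A reader might infer that the majority of withdrawal events are lost. The documents do not support that. They give no incidence, episode duration or recall period, and an assumed 28-day recall would cover 80% or more of pregnancy days. The SOWS form and the CRF completion guidelines are not in the documents, so a recall period may exist there.

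A reader might also infer that the comparison of withdrawal between arms is invalid. It is not. The SOWS is a mother secondary outcome given on the same schedule in both arms, and it can be analysed under sections 10.3 and 10.3.3, although no hypothesis in section 10.1.2 names it. Non-serious AE reports in an open-label trial are not an obviously better basis for that comparison. Nor do the documents identify the change from weekly to monthly BUP-XR as a period of raised withdrawal risk.

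Finally, a reader might conclude that the SOWS should be given weekly. That would cut against the minimal-assessment rationale in section 4.3.2, and the gap can be closed without it.

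**Conclusion.** The point holds as a gap between the AE rule and the assessment schedule. Withdrawal is taken off a weekly record and assigned to a scale present at about 26-30% of weekly visits in pregnancy and about 9% postpartum, with no provision for the visits in between. What may be missed, or recorded inconsistently across sites, is non-serious withdrawal outside induction that arises between SOWS visits.

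The size in events is unknown. In pregnancy it depends heavily on recall: about 4% of days are covered at one day, and 80-94% at 28 days once overlap is removed. Postpartum the gap persists at every recall tested, with 38% of days covered at best. The visit shares assume delivery at 40 weeks and monthly visits every four weeks. The consequence is incomplete safety ascertainment, not a flaw in the scheduled SOWS outcome.

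**What to change.** Amend section 11.17.2 so that the exemption covers only withdrawal symptoms captured on a SOWS-Gossop completed at that same visit. Withdrawal reported at any other visit goes on the AE form. The existing provisions for precipitated withdrawal and for SAEs stay as they are. In section 10.3.4, add a table of withdrawal AEs by arm beside the scheduled SOWS scores. The two should be shown side by side and not summed, since an episode entered as an AE could also be reflected in the next SOWS.

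The cost is one amended sentence, one table and site retraining. There will be more non-serious AE entries, and because the trial is open-label their reporting may differ by arm, so the table should be read as descriptive safety information.

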10.3.4 Safety Analyses

10.3.4.1 Adverse Events

For mothers, adverse events (AEs), including serious adverse events (SAEs), will be summarized by system organ class and preferred term using MedDRA (The Medical Dictionary for Regulatory Activities). Adverse events will be presented as the number and proportion of participants experiencing at least one incidence of each event and will be presented overall and by treatment

group. Listings of serious adverse events will be provided, sorted by treatment, system organ class, and preferred term. Detail in these listings will include severity, relationship to study drug, and outcome. The number of participants experiencing each type of AE and SAE may be compared between treatment arms using either Fisher's Exact test or Pearson's χ^2 test, as appropriate.

For infants, events will be summarized in a similar way, however, infant death, congenital anomalies in all infants and other infant SAEs in breastfed infants are reportable.

10.3.4.2 *The Hospital Anxiety and Depression Scale (HADS)*

Depression and anxiety scores, as measured by the HADS, will be summarized using descriptive statistics over time by treatment arm. Repeated measures mixed models may be used to compare the treatment groups on the depression and anxiety symptoms from screening/baseline through 12 months postpartum.

10.3.4.3 *Fetus/Delivery-Related Outcomes*

Fetus/delivery-related outcomes will be summarized by treatment arm. Listings may be provided for fetus- or delivery-related outcomes of particular concern and will be broken down by treatment arm.

10.3.4.4 *Birth/Neonatal Outcomes*

Outcomes related to the birth and/or neonate, such as head circumference or the need for resuscitation, will be summarized by treatment arm and listings may be provided for adverse outcomes, as needed.

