Local quality assurance monitors will review study sites and respective study data on a regular basis and will promptly advise sites to report any previously unreported safety issues and ensure that the reportable safety-related events are being followed to resolution and reported appropriately. Staff education, re-training or appropriate corrective action plan will be implemented at the participating site when unreported or unidentified reportable AEs or serious events are discovered, to ensure future identification and timely reporting by the site.

Sponsor's Role in Safety Management Procedures of AEs/SAEs

A NIDA-assigned Medical Monitor is responsible for reviewing all serious adverse event reports. All reported SAEs will generate an e-mail notification to the Medical Monitor, Lead Investigator, and designees. All SAEs will be reviewed by the Medical Monitor in Advantage eClinical and, if needed, additional information will be requested. The Medical Monitor will also report events to the sponsor, pharmaceutical company (Braeburn), and the DSMB. The DSMB will receive summary reports of all adverse events annually, at a minimum. The DSMB or the NIDA assigned Medical Monitor may also request additional and updated information. Details regarding specific adverse events, their treatment and resolution, will be summarized by the Medical Monitor in writing for review by the sponsor and DSMB. Subsequent review by the Medical Monitor, DSMB, FDA and ethics review committee or IRB, the sponsor, or relevant local regulatory authorities may also suspend further trial treatment at a site. The study sponsor, DSMB and FDA retain the authority to suspend additional enrollment and treatments for the entire study as applicable.

Reporting to the Data and Safety Monitoring Board

The DSMB will receive listings of AEs and summary reports of all SAEs at a frequency requested by the DSMB, but at least annually. Furthermore, the DSMB will be informed of expedited reports of SAEs.

[figure not shown]
Regulatory Reporting for an IND study

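### Non-serious injection-site reactions, which only BUP-XR can cause, have no planned place in the by-arm AE tables, the DSMB's AE listings or any other stated summary

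*Combined protocol and SAP*

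**What the plan says.** Sections 7.3.7 and 11.17.2 give the recording route: "Injection site reactions will be documented on the Injection Site Reaction Reporting form". In Table 3 that form has its own row, separate from the AE/SAE row.

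Section 11.17.2 places the injection-site examination among several named assessments, introduced by this sentence: "Safety for this study will be monitored through specific study assessments and medical record abstraction in addition to more standard AE/SAE reporting". After those assessments comes the rule on double recording: "Events captured on study specific forms (e.g., HADS) will not be recorded separately as an AE, unless they meet the SAE definition". The list of reportable events then opens with a limit: "For the purpose of this study and if not described above, these events are required to be reported as an AE/SAE". That list includes "All maternal AEs/SAEs while on study, except as noted below in" a second list of exempt events, and injection-site reactions are not named in the second list.

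Appendix A says the AE form holds the AEs and SAEs that the protocol defines as reportable.

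For analysis, section 10.3.4.1 plans MedDRA tables overall and by treatment group: "Adverse events will be presented as the number and proportion of participants experiencing at least one incidence of each event". The numbers of participants with each type of event "may be compared between treatment arms using either Fisher's Exact test or Pearson's χ^2 test, as appropriate". Sections 10.3.4.2 to 10.3.4.4 add summaries for the HADS, fetal and delivery outcomes, and birth and neonatal outcomes.

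For monitoring, Appendix A states: "The DSMB will receive listings of AEs and summary reports of all SAEs at a frequency requested by the DSMB, but at least annually". Section 17.3 of Appendix B describes the same listings as covering reportable AEs.

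**The concern.** The trial is open-label with no dummy injection (section 4.3.1), so only BUP-XR participants can have an injection-site reaction. A rule that moves this class of event off the AE form therefore affects one arm's AE table and not the other's. Section 4.3.2 justifies the weekly visits partly by the need for close safety monitoring in the first trial of this formulation in pregnant women. Under section 4.2.1, the longest exposure in pregnancy runs from week 6 to week 40, which is 40 − 6 = 34 weekly injections, with up to 52 more postpartum. A by-arm AE table without the injection's own local effects would give an incomplete comparison, and nothing in the analysis section would tell the reader so.

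The routine reviews are affected too. Appendix A has a study clinician review reportable AEs at least weekly for seriousness, severity and causality, and section 17.2.2 has the Medical Monitor review AEs weekly for trends. Reactions held only on a separate form fall outside both reviews as described.

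**Working it through.** No figure in the plan bears on this point, so the check sets the rules side by side.

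1. **Where the event is recorded.** Sections 7.3.7 and 11.17.2 both name the Injection Site Reaction Reporting form. Neither adds that a reaction is also an AE.
2. **Whether the rule reaches that form.** The rule covers events on study-specific forms and gives the HADS only as an example. The injection-site examination is in the same run of assessments as the HADS, above the rule. On a plain reading the form is covered.
3. **Whether another sentence brings the reactions back.** The reportable list applies to events not already described, and these reactions are described just above it. Where the authors wanted an exception they wrote one. Precipitated withdrawal is made an AE by name (9.3.1 and 11.17.2), overdose with naloxone rescue is made an SAE (7.3.8), and qualifying infant sedation in breastfed infants is made an SAE (7.3.9). Section 7.3.7 has no such sentence.
4. **What reaches the AE dataset.** The AE form holds only what the protocol defines as reportable. Steps 1 to 3 leave non-serious injection-site reactions out. Serious ones stay in, because the rule itself exempts events that meet the SAE definition.
5. **What the outputs draw on.** The tables in 10.3.4.1 and the DSMB listings are built from AEs. The other subsections of 10.3.4 cover the HADS, fetal and delivery outcomes, and birth and neonatal outcomes. None covers the injection-site form.
6. **What happens in the other arm.** The documents describe no matching form for BUP-SL. A non-serious local complaint on a tablet or film would by default be a maternal AE and be counted. This is an inference, since the documents never mention such complaints. The omission for BUP-XR does not depend on it.

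**Scale.** About 200 participants randomized 1:1 gives 200 / 2 = 100 in the BUP-XR arm. If a fraction r of them had at least one non-serious reaction, 100 × r participants would be missing from that row of the AE table. For assumed r of 5%, 10%, 20% and 30%, that is 5, 10, 20 and 30 participants. The documents give no value for r, so these figures show only how the omission scales.

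**The case against.** The strongest reply is that the exclusion is not explicit. The rule names only a symptom scale. The bullet on maternal AEs is broad, and injection-site reactions are not among its exceptions. Opioid overdose also has its own assessment above the rule, yet it is exempted again by name, which would be unnecessary if having a form were enough. Sections 17.2.1 and 17.8 say that all AEs are collected and reported. This has some force: the text leaves room for doubt, and sites could read it differently. It does not remove the problem. Sections 17.2.1 and 17.8 defer to the protocol, which leads back to 11.17.2, and if sites differ, reactions would be AEs at some and not at others.

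A second reply is that nothing is lost. The reactions are a named safety measure, examined in person and recorded. The Medical Monitor presents safety data to the DSMB (11.17.2), and a standalone SAP mentioned in section 10.4.2, which is not among these documents, might add a table. All of this is possible, but no section at hand plans it.

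A third reply is that separate reporting is defensible, because active site examination occurs only in the BUP-XR arm and pooling would build in unequal ascertainment. That stands, and it is why the fix asks for both displays.

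Three stronger readings go too far:

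- A reader might infer that severity and relatedness summaries for BUP-XR are understated. Section 10.3.4.1 plans that detail only for the SAE listings, which still include serious reactions.
- A reader might infer a hidden gap in overall AE incidence. If 60% of each arm had some other AE, and reactions occurred independently in 10% to 30% of BUP-XR participants, the BUP-XR figure would be 1 − 0.40 × 0.90 = 64% to 1 − 0.40 × 0.70 = 72%, or 4 to 12 points above 60%. All these inputs are assumed, and 10.3.4.1 plans no row for any AE.
- A reader might infer that the DSMB is denied the data. The documents show only that the stated AE listings would not carry them.

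**Conclusion.** The point holds on a plain reading of 11.17.2. Non-serious injection-site reactions are kept off the AE form and are given no other planned summary, so they would be absent from the by-arm MedDRA AE tables and the stated DSMB listings of reportable AEs. The omission falls on BUP-XR alone. It covers non-serious reactions only, and it concerns reporting, not data collection. The conclusion rests on treating the injection-site form as a study-specific form in the sense of the rule. Its place in the section supports this, but the rule does not say so by name. Without a reaction rate in the documents, no size of effect can be stated. The change should be made because the plan as written leaves a safety measure specific to one arm out of every stated summary and is open to uneven use across sites.

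**What to change.** - **Section 11.17.2:** exempt injection-site reactions from the rule on study-specific forms, or state that the form is mapped into the AE dataset. Either wording also settles how sites should read the maternal AE bullet.
- **Section 10.3.4.1:** state that these reactions are MedDRA-coded and shown by arm, with AE summaries displayed with and without administration-site events, because active examination occurs only in the BUP-XR arm.
- **Section 10.3.4:** add a summary of reactions in the BUP-XR arm, separately for the weekly and monthly formulations.
- **DSMB report:** include that summary.

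The cost is wording in these sections, coding of a form already collected, and a few more tables. No new visits or data are needed. The BUP-XR AE figures will look slightly less favourable, and the paired display lets readers see how much of that comes from events only an injection can cause.
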